The actual performance of the sTMS device in clinical practice is more likely to be reflected by the results of the PP analysis in the non-treatment naive population. These are the subjects who are most likely to seek sTMS treatment based upon the recommendation of their physicians. **Subjects who had attempted or completed prior antidepressant treatment in the current episode (ATHF 1 - 6) demonstrated significantly greater benefit from sTMS treatment compared to sham (-8.58 vs. -4.25, $p=0.005$), while treatment-naïve subjects (ATHF 0) showed no significant difference between active and sham (-9.76 vs. -10.08; $p=0.28$).** **Subjects who had attempted or completed prior antidepressant treatment in the current episode also had a statistically significantly higher response rate (34.2% vs. 8.3%, $p= 0.017$) and a numerically but not significantly higher remission rate (13.2% vs. 5.6%, $p=0.26$) with active treatment than with sham; treatment-naïve subjects showed the opposite pattern.** The magnitude of the improvement seen in this population is similar to or greater than that seen with medication and already-approved rTMS devices.

One conclusion from this study was that poor quality EEG recordings (i.e. high variability, poor electrode preparation) could result in the assignment of an inappropriate treatment IAF, and that patients treated at a frequency greater than 1 HZ from their IAF did not respond as well as those treated at the correct value. Consequently, NeoSync modified the NEST software to include an automatic EEG quality qualification process to improve the assignment of the correct treatment frequency. **The present study is designed to confirm that treatment with the modified software produces clinical improvement comparable to that demonstrated in the previous study in the non-treatment naive PP sub population.** Therefore, only patients who failed to respond to at least one AD medication in the current episode (i.e. treatment resistant) will be studied in this trial.

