Qualified subjects will be randomized to either active sTMS or sham treatment groups in a 1:1 ratio on an individual basis. Randomization will be stratified by site in blocks of 10 determined by a computer generated randomization table defined prior to the start of the trial. Each site will be given a set of 10 randomized PPMs. Treatment will be initiated on Day 1 of the study. Subjects will come to the clinic for 5 daily treatment sessions for a total of 6 “treatment” weeks. A visit interval of 5-10 calendar days has been set for each “treatment” week to accommodate visit scheduling flexibility. Treatment will be discontinued at the end of Week 6 (30 treatment sessions). Subjects will be clinically evaluated for safety and efficacy at the end of each of the six weekly treatment courses.

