11.4 ANALYSIS PLAN

Definition of Primary Endpoint

The primary endpoint is clinical response, defined by 50% or greater reduction on the HAM-D₁₇ total symptom scores through 6 weeks of treatment.

Statistical Hypotheses

We will test the null hypothesis that the active sTMS treatment group does not differ from the sham group in the proportion of subjects who show 50% or greater improvement from baseline to Week 6 on the HAM-D₁₇ total score. The corresponding alternative hypothesis is that the active sTMS treatment group has a greater proportion of patients than the sham group with respect to the proportion of subjects who show 50% or greater improvement from baseline to Week 6 on the HAM-D₁₇ total score. The hypotheses can be expressed numerically as:

$$H_0: \pi_A - \pi_S = 0$$

and

$$H_a: \pi_A - \pi_S \neq 0$$

where π_A is the proportion of subjects who show 50% or greater improvement in mean HAM-D₁₇ total score from baseline (Day 0) to Week 6 for the active treatment and π_S is the equivalent value for the sham-controlled group.

Sample Size Calculation

The calculation of sample size requirements for this confirmatory study is based on the results observed in the PP analysis of non-Naïve subjects enrolled in the previous NEST trial. In that population, 34% of subjects treated with active sTMS were categorized as responders, whereas only 8% of sham treated subjects responded. Assuming true population response rates of 34% for sTMS and 8% for Sham, power analysis indicates that a PP sample size of 92 subjects (46 subjects per treatment group evaluable at week 6) yields 81% power to demonstrate superiority of sTMS, where the statistical test is Fisher's exact test at a two-sided 0.05 level of significance. A total of 120 subjects will therefore be enrolled in the study to account for potential drop-outs and noncompliance prior to Week 6.

Adaptive Sample Size Re-estimation

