The following analyses will be carried out for each of the ITT and PP (primary) populations. There will be no imputation for missing data or adjustments for multiple comparisons.

Additional Endpoints to be studied are:

- The change in mean symptom scores on the HAM-D₁₇ through 6 weeks of treatment
- The change in mean symptom scores on the MADRS through 6 weeks of treatment.
- Clinical response, defined by 50% or greater reduction on the MADRS total symptom scores through 6 weeks of treatment.
- Effectiveness of Blinding questionnaire

Descriptive statistics (sample size, mean, median, quartiles, standard deviation, minimum, maximum) of the mean change in HAM-D₁₇ and MADRS from baseline to Week 6 will be presented. Change from baseline in the HAM-D₁₇ and MADRS total scores will be compared across treatment groups using a MMRM model with terms for treatment, investigative center, visit, and the treatment by visit interaction (visits in the open-label phase will be excluded for the primary double-blind analysis). The model will also include baseline HAM-D₁₇ (or MADRS) score as a covariate and subject will be a random effect. An unstructured covariance matrix will be used for the within-subject correlation. Kenward-Rogers'

approximation will be used to estimate degrees of freedom. The LSMEANS statement for the treatment-by-visit interaction will be employed to examine differences across treatments at specific time points, with the focus being on the Week 6 change from baseline. Parameter estimates will be presented and two-sided 95% confidence intervals will be constructed using model estimates for the mean and residual error. Tests of hypotheses will be two-sided and will be based on the contrasts between active sTMS and sham within the model.

For MADRS response rate through 6 weeks of treatment, the number and percentage of responders will be calculated and will be compared in a similar manner as the primary endpoint. Tests of hypotheses will be two-sided and will be based on the contrasts between active sTMS and sham within the model.

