The primary hypothesis in the double-blind phase will be tested using Fisher's Exact test on the ITT and PP analysis populations. For the ITT population, there may be missing data at Week 6 due to, for example, patients prematurely withdrawing from the study. The first analyses for the ITT population will use available data. As a supportive sensitivity analysis, multiple imputation will be used to assess the robustness of the primary endpoint findings relative to missing data. Specifically, multiple imputation using the linear regression approach will be used to impute missing HAM-D¹⁷ across visits via SAS PROC MI; included as covariates in the linear model will be age, sex, race, education level, HAM-D17 measured at previous visits, investigative center, baseline MMSE, baseline IDS-SR, baseline C-SSRS, and ATHQ categorizations. Ten complete datasets will be created (the linear regression approach to multiple imputation assumes monotone missing data pattern; if such a pattern does not exist, then prior to each of the 10 linear regression imputations, any non-monotone missing data will first be imputed via the Monte-Carlo Markov Chain approach to create a monotone missing data pattern). Once 10 complete HAM-D¹⁷ datasets are generated, the determination of whether the patient achieved imputed clinical response at Week 6 will be calculated for each patient with missing data within each imputed dataset. The z-test for proportions with continuity correction (which yields very similar results to Fisher's Exact test) will then be applied to each of these 10 datasets to compare treatments on

the incidence of Week 6 clinical response. The numerator and denominator of the 10 continuity-corrected z -statistics will then be combined into a single continuity-corrected z-statistic using SAS PROC MIANALYZE. The resulting p-value from this z-statistic, assessing overall significance of treatment difference on clinical response rate at Week 6, will be calculated.

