The following secondary measures are to be considered for labeling. They will be analyzed using the gatekeeper (sequential) strategy to control for multiple comparisons by pre-specifying the order of testing (Westfall and Krishen, 2001). If the primary analysis is significant, these outcomes will be tested in the order listed below, each at the 0.05 alpha level. Testing for label consideration will cease when the first outcome results in a two-sided p-value greater than 0.05.

- Change from Baseline on the HAM-D¹⁷ score at Week 6;
- Change from Baseline on the MADRS score at Week 6;
- Clinical response, defined by 50% or greater reduction on the MADRS total symptom score at Week 6.

Treatments will be compared on the mean change from baseline HAM-D¹⁷ and MADRS scores at Week 6 using analysis of covariance adjusting for the baseline value of the given endpoint. Treatment group comparisons on the proportion of subjects who achieve MADRS clinical response at Week 6 will be carried out using Fisher's Exact test. Tests of hypotheses will be two-sided.

Assessment of investigator center-by-treatment interaction will be carried out using Breslow-Day test for the MADRS clinical response at Week 6 and using analysis of covariance with the independent variables of treatment group, investigative center, and the treatment-by-investigative interaction for change from baseline in HAM-D¹⁷ and MADRS at Week 6. Again, a non-significant interaction (using a 0.15 level of significance) or a significant interaction deemed only quantitative in nature supports the pooling of results across centers for the analyses on these secondary endpoints.

Multiple imputation for the ITT population for each endpoint will be carried out using linear regression in a similar manner as for the primary endpoint. For MADRS clinical response, the overall significance of the difference between treatment groups across the imputed datasets will be carried out in the same manner as for the primary efficacy endpoint. For the mean change from baseline at Week 6 for each of HAM-D¹⁷ and MADRS, analysis of covariance comparing treatments adjusting for the baseline value of the endpoint will be carried on each imputed dataset with the results being combined across imputed datasets using PROC MIANALYZE to obtain one overall assessment of treatment difference on the mean endpoint, adjusting for baseline.

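### Antidepressant treatment history is recorded before randomization, but no efficacy comparison adjusts for it: a minor, nearly free improvement

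*Protocol*

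**What the plan says.** **What NEST reported.** Protocol 1.1 splits the earlier trial's PP results by treatment history: "Subjects who had attempted or completed prior antidepressant treatment in the current episode (ATHF 1 - 6) demonstrated significantly greater benefit" with sTMS than with sham, while treatment-naive subjects (ATHF 0) showed no significant difference.

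**When history is collected.** Protocol 5.1 has the ATHF for the current episode verified at screening. Appendix I and Protocol 7.2 (item 10) also place the instrument at screening. Item 10 says the ATHQ predicts outcome with somatic treatments.

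**Who can enter.** Inclusion criterion 3 (Protocol 4.1) requires inadequate response to at least one antidepressant in the current episode, at ATHF confidence level 3 or more. It sets no upper limit on level or on the number of failed drugs.

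**Allocation.** "Randomization will be stratified by site in blocks of 10" (Protocol 3, repeated in 5.3). Treatment history is not a stratum.

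**Efficacy comparisons.**
- Primary response: Fisher's exact test, unadjusted (Protocol 11.5; SAP, Analysis of Primary Efficacy Endpoint).
- Week 6 change in HAM-D17 and MADRS, SAP section H: compared "using analysis of covariance adjusting for the baseline value of the given endpoint".
- The same endpoints in Protocol 11.5: "MMRM model with terms for treatment, investigative center, visit, and the treatment by visit interaction", plus the baseline score.

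**Where history does appear.** The multiple-imputation model for the ITT set includes "baseline IDS-SR, baseline C-SSRS, and ATHQ categorizations" (SAP section F). ATHQ history is a subgroup factor (SAP section G). History is summarized at baseline (Protocol 11.2; SAP section E). None of these adjusts the overall treatment comparison.

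**The concern.** A baseline variable that predicts outcome, left out of a linear model, leaves its share of the variance in the error term. It also leaves any chance difference between arms in the treatment estimate. Here the variable is already on the case report form, and the protocol itself calls the instrument predictive.

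The comparisons with most to gain are the two Week 6 change-score tests. The SAP tests them in sequence for labelling once the primary test succeeds.

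There is a second, smaller reason. The primary population is per protocol, defined partly by compliance after randomization, and the SAP expects about 23% of enrolled subjects to fall outside it. Randomization does not guarantee balance in that subset. Adjusting for a pre-randomization prognostic factor is a partial check on this, not a cure.

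**Working it through.** **1. The plan's own figure.** "Assuming true population response rates of 34% for sTMS and 8% for Sham", "a PP sample size of 92 subjects (46 subjects per treatment group evaluable at week 6) yields 81% power". With n = 46, d = 0.26, mean rate 0.21 and a continuity correction:

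- null SE = √(2 × 0.21 × 0.79/46) = 0.0849
- alternative SE = √((0.34 × 0.66 + 0.08 × 0.92)/46) = 0.0805
- power = Φ[(0.26 − 1/46 − 1.96 × 0.0849)/0.0805] = 81.4%

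Full enumeration of Fisher's test gives 83.6%. Enrolment: 92/(1 − 0.23) = 119.5, so 120. The stated design reproduces.

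**2. What NEST can and cannot say (Protocol 1.1).** Its contrast is ATHF 0 against ATHF 1–6 pooled, with no split within 1–6.

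| PP mean HAM-D17 change | Naive | Non-naive | Gap |
|---|---|---|---|
| Sham | −10.08 | −4.25 | 5.83 |
| Active | −9.76 | −8.58 | 1.18 |

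One common covariate term works on the arm-averaged gap: (5.83 + 1.18)/2 = 3.5 points. For ITT response, the sham gap is 48.6 − 15 = 33.6 points. The active gap is about 0 (27.2% overall, 27% without naive subjects), so the average is about 17 points. Criterion 3 removes ATHF 0, so both averages serve only as outer bounds.

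**3. Variance explained in the change models.** Assumptions: a two-level factor split 50/50, and SD = √((7.33² + 4.74²)/2) = 6.2 from the NEST non-naive completers. For a gap D:

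R² = 0.25 × D²/6.2²; equivalent extra subjects = 92 × (1/(1 − R²) − 1)

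| D (points) | R² | Equivalent subjects of 92 |
|---|---|---|
| 1 (assumed) | 0.7% | 0.6 |
| 2 (assumed) | 2.6% | 2.5 |
| 3.5 (outer bound) | 8.0% | 8.0 |

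These are before the loss of one degree of freedom. A split other than 50/50 lowers R² for the same D.

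**4. Power of the change tests.** Formula: Φ[δ/(6.17 × √(1 − R²) × √(2/46)) − 1.96], with δ taken from the NEST non-naive differences: 8.58 − 4.25 = 4.33 (PP) and 7.39 − 4.59 = 2.80 (Completers).

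| R² | δ = 4.33 | δ = 2.80 |
|---|---|---|
| 0 | 92.0% | 58.5% |
| 1% | 92.2% | 59.0% |
| 4% | 93.0% | 60.3% |
| 9% | 94.1% | 62.6% |

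**5. Chance imbalance.** For a 50/50 factor, the SD of the between-arm difference in prevalence is √(2 × 0.25/46) = 0.104. An imbalance of 1.96 SD is about 20 points. It shifts the response difference by 0.204 × gap. Assumed gaps of 6, 10 and 14 points give 1.2, 2.0 and 2.9 points. On the change score, 0.20 × 1 to 0.20 × 2 gives 0.2–0.4 points, and 0.7 at the outer bound.

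**6. Primary response test.** In 20,000 simulated trials per scenario, Fisher's test was compared with a stratified CMH test with continuity correction. Overall rates were held at 34% and 8%; the rates by stratum are assumed.

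| Sham rates by stratum | Active rates by stratum | CMH | Fisher |
|---|---|---|---|
| 8%/8% | 34%/34% | 82.9% | 83.8% |
| 5%/11% | 31%/37% | 82.8% | 83.5% |
| 3%/13% | 29%/39% | 83.5% | 83.8% |
| 1%/15% | 24%/44% | 84.9% | 83.9% |
| 1%/15% | 34%/34% | 83.0% | 83.5% |

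Monte Carlo error is about 0.3 points. The SD of the risk difference moves from 0.080 to between 0.079 and 0.081. With no treatment effect, Fisher's test rejected in 1.5% of trials (8% throughout), 1.6% (1%/15% by stratum) and 2.8% (11%/31% by stratum).

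**The case against.** The strongest reply is that the sponsor has already dealt with the NEST finding by restricting entry. A reader might infer from NEST that history will strongly drive sham outcome in this trial too. The documents do not support that. The NEST contrast is between naive and treated subjects, naive subjects cannot enter, and nothing shows a gradient within ATHF 3 or higher. The quoted NEST sentence also concerns benefit relative to sham, which is effect modification, and SAP section G already looks at that by ATHQ history. This part of the reply stands.

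A reader might also infer that the unadjusted primary test is invalid or materially underpowered. It is neither. Randomization already allows for chance imbalance in the test and its interval, the simulated false-positive rates stay below 5%, and stratifying changes power by about −1 to +1 point. Imbalance would also be visible in the planned baseline tables.

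Use of ATHQ in the imputation model is weak evidence of prognostic importance, since that list also holds race, education and MMSE. ATHF confidence level (adequacy of dose and duration) and number of failed drugs are different scales, so the covariate has to be defined rather than assumed.

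What the reply does not answer is the protocol's own statement that the ATHQ is predictive, together with the absence of any adjusted comparison. A baseline-only ANCOVA is legitimate, but it leaves out a predictor that is already in hand.

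**Conclusion.** The point holds as a minor improvement, not as a correction of the primary analysis. No efficacy comparison adjusts for treatment history, and adding it to the change models would probably recover the equivalent of about 1–3 evaluable subjects, with 8 as an outer bound. For R² up to 4%, power on a change test rises by at most about 2 points. The primary conclusion is unlikely to change.

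These sizes rest on an assumed 1–2 point gradient, an assumed even split, and an SD borrowed from NEST completers that is not a baseline-adjusted residual SD. If the gradient among eligible subjects is close to zero, so is the gain. The case rests on low cost and on timing: specified now, the analysis is credible; added after an imbalance is seen, it would be post hoc.

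**What to change.** Before unblinding, amend the SAP as follows.

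1. Define one pre-randomization resistance level from the ATHF/ATHQ, for example one versus two or more failed adequate antidepressants in the current episode. SAP section E lists subjects resistant to 2, 3, and 4 or more drugs, so the category for exactly one must be written in.
2. Add that level as a fixed term in the Week 6 HAM-D17 and MADRS change models (SAP section H; the MMRM in Protocol 11.5).
3. Keep Fisher's exact test as primary.
4. Add one supportive response analysis: logistic regression on treatment, baseline HAM-D17 and resistance level, reported as a standardized risk difference with a 95% confidence interval, in PP and ITT. About 46 × 0.34 + 46 × 0.08 = 19 responders are expected, so the model should carry no further covariates.

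Cost: SAP wording and one degree of freedom in models with about 92 subjects. No new data, visits or patients are needed.

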2 STUDY OBJECTIVE

The primary objective of this study is to confirm the safety and effectiveness of synchronized TMS (sTMS) therapy in subjects with Major Depressive Disorder who have not responded adequately to at least one antidepressant medication in the current episode.

3 STUDY DESIGN

This clinical trial is a prospective, randomized, double-blinded, sham-controlled study to confirm the safety and efficacy of sTMS in subjects with Major Depressive Disorder who have not responded to at least one anti-depressant medication in the current episode. This is a multicenter study in which approximately 120 subjects will be enrolled and undergo sTMS therapy in the trial. Randomized subjects will receive 5 daily treatments per treatment week for 6 treatment weeks (total of 30 treatments). Following completion of their treatment period, subjects who have not remitted (remission defined as a HAM-D₁₇ score of ≤ 7 (Zimmerman et al., 2004)) may be offered an additional 6 weeks of open label sTMS treatment, if the clinician feels this is appropriate for that subject.

Alternatively, if the clinician feels it is not appropriate for the subject to participate in the open label sTMS follow-up, the subject chooses not to participate in the open label follow-up or if the subject has remitted in the blinded phase, subject will be deemed to have completed participation in this study.

For subjects who participate in the open label sTMS follow-up, a weekly evaluation will be conducted at Week 7, 8, 9, 10, 11 and 12.

After signing informed consent, subjects who qualify for enrollment based upon assessments performed at Screening will discontinue use of their current antidepressant treatment (if applicable). Subjects must have discontinued the antidepressant medication a minimum of 1 week prior to initiation of treatment with the sTMS. An additional evaluation (Baseline) will be performed at least one week following screening to determine whether the protocol eligibility criteria are still met before randomization and the first treatment. Subjects who show an improvement of more than 5 points on the HAMD-17 between the screening and baseline assessments will be excluded from the study.

Qualified subjects will be randomized to either active sTMS or sham treatment groups in a 1:1 ratio on an individual basis. Randomization will be stratified by site in blocks of 10 determined by a computer generated randomization table defined prior to the start of the trial. Each site will be given a set of 10 randomized PPMs. Treatment will be initiated on Day 1 of the study. Subjects will come to the clinic for 5 daily treatment sessions for a total of 6 “treatment” weeks. A visit interval of 5-10 calendar days has been set for each “treatment” week to accommodate visit scheduling flexibility. Treatment will be discontinued at the end of Week 6 (30 treatment sessions). Subjects will be clinically evaluated for safety and efficacy at the end of each of the six weekly treatment courses.

4 SUBJECT POPULATION

Approximately 120 male and female subjects, aged 22 to 65 years who are suffering from Major Depressive Disorder will be enrolled in the trial. Randomized subjects will receive sTMS or sham treatment, with randomization in a 1:1 ratio with approximately 60 subjects enrolled per arm. Subjects who have provided informed consent, who are capable of comprehending the nature of the study, and who are likely to comply with the visit schedule are to be entered into the study provided they conform to the following criteria.

